## Study aims

Primary Outcome:

- 1) Does early administration of insulin glargine result in a shorter ICU length of stay when compared to usual care for the treatment of diabetic ketoacidosis?

Hypothesis: Early administration of insulin glargine will result in shorter ICU length of stay when compared to usual care in patients with DKA.

Secondary Outcomes:

- 1) Does early administration of insulin glargine result in a shorter hospital length of stay (defined as time between start of insulin infusion and discharge from hospital) when compared to usual care for the treatment of diabetic ketoacidosis?

Hypothesis: Early administration of insulin glargine will result in shorter hospital length of stay when compared to usual care in patients with DKA.

- 2) Does early administration of insulin glargine result in a faster recovery from DKA (defined as blood glucose < 200 and two of: Anion Gap  $\leq$  12, Serum Bicarbonate  $\geq$  15 mEq/L, or pH > 7.3) when compared to usual care for the treatment of diabetic ketoacidosis?

Hypothesis: Early administration of insulin glargine will result in a faster recovery from DKA (defined as blood glucose <200 and two of: Anion Gap  $\leq$  12, Serum Bicarbonate  $\geq$  15 mEq/L, or pH > 7.3) when compared to usual care for the treatment of diabetic ketoacidosis.

- 3) Does early administration of insulin glargine result in a shorter duration of elevated anion gap (defined as time with anion gap > 12) when compared to usual care for the treatment of diabetic ketoacidosis?

Hypothesis: Early administration of insulin glargine will result in a shorter duration of elevated anion gap (defined as time with anion gap > 12) when compared to usual care for the treatment of diabetic ketoacidosis.

- 4) Does early administration of insulin glargine result in a shorter duration of time on IV insulin infusion when compared to usual care for the treatment of diabetic ketoacidosis?

Hypothesis: Early administration of insulin glargine will result in a shorter duration of time on IV insulin infusion when compared to usual care for the treatment of diabetic ketoacidosis.

- 5) Does early administration of insulin glargine result in a lower prevalence of rebound hyperglycemia, defined as blood glucose > 180 mg/dL in the 24 hours after IV insulin infusion discontinuation, when compared to usual care for the treatment of diabetic ketoacidosis?

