## **Background, Rationale, Significance**

In 2014, there were 168,000 hospitalizations for DKA, and the average length of stay was 3.4 days in 2009. The estimated annual direct medical expense and indirect cost is 2.4 billion dollars per year. DKA is a potentially life-threatening condition due to its ability to cause metabolic acidosis, electrolyte imbalances, and dehydration. While DKA treatment protocols differ from institution to institution, the goals of treatment remain the same --- resolution of acidosis, dehydration, and hyperglycemia. Following fluid resuscitation, correction of hyperglycemia with insulin therapy is the mainstay of treatment. Intravenous (IV) insulin infusions with regular insulin are commonly used due to its short half-life of 30 to 60 minutes and resulting titratability. Treatment is then continued with subcutaneous (SC) insulin once the acidosis and anion gaps have cleared and the patient's hemodynamics and electrolytes abnormalities have resolved. At Regions Hospital, the current criteria for transitioning from IV to SC insulin include meeting the following criteria: 1) fasting blood glucose levels are stable between 180-250 mg/dL for at least 4 hours, 2) vital signs, potassium, and sodium levels are stable and within the normal range, 3) the metabolic acidosis has cleared (anion

gap  $<15$ , and either arterial pH  $\geq 7.3$  or venous pH  $\geq 7.27$ ), and 4) the patient is able to eat regular meals. Traditionally, when SC insulin is initiated, the IV insulin infusion is stopped two hours later. However, the timing of SC initiation has becoming more controversial in recent years. The 2019 American Diabetes Association Standards of Care recommend transition of patients from IV to SC insulin requires administration of basal insulin 2–4 h prior to the intravenous insulin being stopped to prevent recurrence of ketoacidosis and rebound hyperglycemia. However, the 2014 Joint British Diabetes Societies Inpatient Care Group recommend continuing a patient's home basal insulin during the initial management of DKA to prevent rebound hyperglycemia and to avoid extending length of stay. Several recent papers have examined early basal insulin administration as adjunct therapies with IV insulin infusions for the treatment of hyperglycemia and DKA.

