Lastly, Rappaport et al. (2019) conducted a single-center, retrospective cohort study of 106 admissions for DKA comparing early vs late initiation of basal insulin. Patients admitted to the MICU who were treated with home-dose basal insulin prior to DKA resolution and within 24 hours of IV insulin infusion initiation ( $n = 33$ ) were compared to patients who were initiated on basal insulin within 6 hours before or any time after IV insulin infusion discontinuation ( $n = 73$ ). Transition from IV insulin infusion to subcutaneous insulin was not addressed in a protocol and was left to the discretion of the provider. Patients were excluded if they had surgery within 48 hours of IV insulin infusion, were pregnant, were in vasopressor dependent shock, or had another indication for insulin therapy. Patients in the early group had initial daily doses of basal insulin of 0.48 U/kg (IQR: 0.34 – 0.62) compared to 0.44 U/kg in the late group. Patients in the early insulin group had their first dose of basal insulin 2.5 hours (IQR: 0.4 – 6.4) after IV insulin infusion initiation. There was no difference in transitional failure (early group: 6% vs late: 10%;  $p = 0.717$ ), rebound hyperglycemia (early: 81% vs late: 88%; OR: 0.59, CI: 0.16 – 2.25), hypoglycemia events (early: 33% vs late: 55%; OR: 0.41, CI: 0.16-1.05); time to anion gap closure: (early: 7.8h vs late: 9.1h;  $p = 0.73$ ), length of ICU stay (early: 34h vs late: 33.3h,  $p = 0.83$ ), or hospital length of stay (early: 2 days vs late: 2 days,  $p = 0.9$ ). There was a statistically significant decrease for time on IV insulin infusion (early: 13.8h vs late: 17.1h,  $p = 0.04$ ).

Preliminary research at Regions Hospital determined that in 40 randomly selected patients admitted for DKA in 2019, the mean dose of basal insulin initiated was 0.39 units per kilogram, and it was administered a mean of 22.4 hours after initiation of the IV insulin infusion and 1.86 hours prior before discontinuation of IV insulin, which is consistent with ADA recommendations

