### Enrollment

Once the patient is randomized, the CCRC intern will notify the ED pharmacist who will determine if patient is currently taking basal insulin and, if they are taking basal insulin prior to admission, will verify the home basal dosing. CCRC research staff will be notified of the dosing order from the randomization and will place the appropriate order. The patient will either receive 0.2 u/kg insulin glargine, current (prior to admission) basal insulin dose, or no additional treatment study protocol. CCRC staff will abstract the study data points from the patient’s EMR while the patient is in the Emergency Department, throughout their hospital stay, and again at the time of discharge. The ED pharmacist will time the insulin glargine dose to be administered optimally within two hours after initiation of the IV insulin infusion.

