### **Interventions and Treatments**

#### Intervention group-specific

For patients who are randomized to the intervention group, subcutaneous insulin will be ordered as follows:

Prior to administration basal insulin (generic)	Prior to administration basal insulin (brand)	Dose equivalent of insulin glargine
Insulin glargine	Lantus; Basaglar, Semglee	1:1
Insulin degludec	Tresiba	1:1
Insulin detemir	Levemir	1:1
None	None	0.2 units/kg

If the patient is in the intervention group, the ED pharmacist and/or research intern will determine if the patient was taking basal insulin prior to admission. If the patient was not taking basal insulin prior to admission, the patient will receive 0.2 units/kg insulin glargine. If the patient was taking basal insulin prior to admission, the patient will receive their home insulin glargine dose.

Once the appropriate dose is determined, the research team will order the randomization dose of study medication and the ED pharmacist will time the study medication to begin within 2 hours after initiation of the IV insulin infusion. The dose will come from IV pharmacy and dispensed in a 1 mL insulin syringe. These syringes are then tubed to the ED. CCRC interns may facilitate this process by picking up the dose from the ED pharmacy or watching the tube stations closely for the dose to arrive, as nurses are sometimes too busy to check these stations on a regular basis. Once the insulin is provided, the nurse will administer the dose. Since the dose if not on basal insulin at baseline is weight-based, a current weight will be taken if not already done at admission. Research staff will ask the RN to complete this.

Research interns will complete follow-up evaluation of incidence of hypoglycemia or hyperglycemia after IV insulin infusion discontinuation. This step will be done in conjunction with one of the study investigators.

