### **Setting/Environment/Organizational feasibility**

The study will be conducted at Regions Hospital. The study will primarily take place while the patient is in the ED, but the study intervention may take place in the ICU if the patient is quickly admitted. The ED pharmacists can oversee ICU medication orders, and the ICU pharmacists will also be trained about this study. This location is appropriate as this study is designed to assess the efficacy and safety of early basal insulin administration versus standard of care for the treatment of DKA. The department heads for endocrinology, emergency medicine, critical care, internal medicine and pharmacy were contacted and have endorsed providing support for this study. The Department of Endocrinology was consulted on providing recommendations for both the dosing of basal insulin as well as the timing of basal insulin initiation in relation to starting the IV insulin infusion. Furthermore, the ED pharmacists, ICU pharmacists, and floor pharmacists have a close working relationship, and communicate with each other daily. All three study investigators have spent time working as ICU pharmacists.

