### **Risks and Benefits**

Potential risks to the patient include hypoglycemia with the administration of both basal and regular insulin administration, however, no study that has examined early basal insulin in combination with IV insulin has shown an increase in the risk of hypoglycemia. Standard of care for patients with DKA includes an overlap of basal and regular insulin for approximately two hours; this ensures that the basal insulin has time to start working before stopping the regular insulin. In our study, patients will have a longer duration of overlap of basal and regular insulin as the basal insulin will be given earlier in the patient's treatment course. Patients with DKA who are receiving IV insulin

infusions, whether participating in this study or not, undergo frequent blood glucose monitoring and have the IV insulin infusion titrated appropriately to prevent hypoglycemia. Potential benefits to the patient and society include shorter hospital and ICU lengths of stay, faster time to resolution of DKA, and less rebound hyperglycemia.

For study patients randomized to the SOC group, the only potential for change in standard care would be if a provider who *would* have deviated from the Regions Hospital DKA Protocol were the patient not in the study *does not* deviate from it if the patient is in the study, due to education about the importance of adhering to the SOC DKA Protocol. (For example, a physician might give SC glargine before the patient meets all criteria for it in the DKA Protocol.) However, as the DKA Protocol is evidence-based, peer-reviewed, and created for optimal patient safety and outcomes, this should not be considered a risk. If, for whatever reason, a study patient in the SOC arm needs treatment that directly contradicts the SOC DKA Protocol, the patient will be withdrawn from the study to ensure patient care and safety are the first priority. In looking at existing data to inform this study protocol, only 3 of 45 patients with DKA at Regions Hospital received SC glargine prior to what the protocol dictates.

All adverse events and serious adverse events will be reported to the IRB within the required time windows.

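### Intervention patients on home basal insulin receive a full home dose about 2 h after infusion start whenever they last injected; that time is neither checked nor recorded, leaving a small, avoidable risk of stacked long-acting doses

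*Combined protocol and SAP*

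**What the plan says.** The dosing rule is under Intervention group-specific: "If the patient was taking basal insulin prior to admission, the patient will receive their home insulin glargine dose". The table there converts glargine, degludec and detemir one to one. The only clock is the infusion: the dose is to be given within 2 h of its start, with a 30-minute tolerance in the Inclusion Criteria.

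Under Enrollment, after randomization, the ED pharmacist establishes whether the patient uses basal insulin and, if so, "will verify the home basal dosing". The data form (Variable list, sources, and data collection) holds basal use as yes/no, the home insulin dose, and the time and amount of the glargine given in hospital. It has no field for the time of the last home dose. The Exclusion Criteria cover pumps and combination products, but not a recent basal dose.

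Risks and Benefits notes that "patients will have a longer duration of overlap of basal and regular insulin" and relies on frequent glucose checks and titration of the infusion. Setting/Environment/Organizational feasibility says Endocrinology advised on basal dose and on "timing of basal insulin initiation in relation to starting the IV insulin infusion"; timing relative to the last home dose is not mentioned.

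**The concern.** The plan's rationale is to resume or continue the home basal regimen. A patient who injected a few hours before arrival has not interrupted it, so an immediate full dose is an addition to the regimen. A long-acting dose cannot be withdrawn once injected. The risk text weighs basal against regular insulin, not one basal dose against another.

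The exposure comes from the trial's timing. Control patients are steered away from long-acting insulin until the site's transition criteria are met, and basal insulin at this site was given "a mean of 22.4 hours after initiation of the IV insulin infusion and 1.86 hours prior before discontinuation of IV insulin". A clinician who sensibly waited in a recently dosed intervention patient would be departing from the written plan. At stake is patient safety in a subgroup that the listed variables cannot identify.

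**Working it through.** **The plan's own figure.** The only related figure is the detectable difference under Sample size, which matters here only for the cost of the fix. With a coefficient of variation of 0.6, the SD on the log scale is sqrt(ln(1 + 0.6²)) = 0.5545. With 66 per arm and alpha 0.05 (two-sided assumed), a ratio of 1.31 has power 0.799 by the normal approximation and 0.793 by the noncentral t; 80% power needs 1.313. The stated ratio of about 1.31 reproduces. The 6.5 h equivalent is taken as stated, since the baseline mean is not given.

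**Inputs for the overlap.**
- D: hours a basal dose acts. The documents call it extended but give no hours. Assumed 24, range 18 to 30.
- h: hours from the last home dose to infusion start. Illustrated at 2, 6 and 12.
- Study dose at 2 h after infusion start (Intervention group-specific).
- Usual first hospital basal dose at 22.4 h, infusion stop 1.86 h later (Background), so mean stop S = 22.4 + 1.86 = 24.26 h. These are means; the spread is not given.

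**Joint action of the two basal doses.** The home dose acts until D − h. With the study dose, joint action is D − h − 2. With usual-care timing it is max(0, D − h − 22.4).

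| D | h | Study dose at 2 h | Usual care at 22.4 h |
|---|---|---|---|
| 24 | 2 / 6 / 12 | 20 / 16 / 10 h | 0 / 0 / 0 h |
| 18 | 2 / 6 / 12 | 14 / 10 / 4 h | 0 / 0 / 0 h |
| 30 | 2 / 6 / 12 | 26 / 22 / 16 h | 5.6 / 1.6 / 0 h |

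Usual care therefore gives no overlap at 18 or 24 h action, but some at 30 h.

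**Where the extra overlap falls.** Overlap remaining after the infusion stops is max(0, D − h − S). The time of the study dose is not in this formula. It applies equally to a control patient, whose hospital basal dose also precedes the stop.
- D = 24, S = 24.26: 0 h for h = 2, 6 or 12, in either arm.
- D = 30, h = 2, S = 24.26: 30 − 2 − 24.26 = 3.74 h, in either arm.
- D = 24, h = 2, early stop at S = 13.8 (the early group's infusion time in the retrospective cohort under Background): 24 − 2 − 13.8 = 8.2 h, in either arm. The study dose gives joint action from 2 to 22 h, of which 11.8 h is during the infusion. A control patient dosed 1.86 h before the stop, at 11.94 h, has joint action from 11.94 to 22 h, of which 1.86 h is during the infusion. The difference is 11.8 − 1.86 = 9.94 h, all before the stop.

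For a given stop time, then, the study dose adds overlap only while the infusion is running.

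**The case against.** The strongest reply is that the added overlap falls when glucose is checked often and the infusion can be turned down. Further safeguards follow: transition requires, among other things, that "fasting blood glucose levels are stable between 180-250 mg/dL for at least 4 hours" and that the patient can eat, and hypoglycemia is followed to 24 h after the infusion. Enrollment happens only when named investigator-pharmacists are on shift, and the attending must permit the approach. The one home-dose study described points the other way: "hypoglycemia events (early: 33% vs late: 55%; OR: 0.41, CI: 0.16-1.05". All of this stands as reason to call the risk small. It does not close the gap. None of these steps requires anyone to ask when the last dose was taken, and that study was retrospective, its interval includes 1, and its description gives no last-dose timing.

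A reader might infer something stronger: that stacked doses leave intervention patients exposed after the infusion, when nothing can be titrated. The documents do not support this. At the same stop time a control patient with the same home dose has the same post-infusion overlap. An excess needs the infusion itself to shorten. The plan hypothesizes that early glargine "will result in a shorter duration of time on IV insulin infusion", and the retrospective cohort reports 13.8 against 17.1 h. But the randomized trial in 61 hyperglycemic patients reports 42 h with early glargine against 35 h without, described as similar.

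It is also fair to object that the share of patients affected is unknown, and that a deferral rule gives up some of the contrast under test.

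**Conclusion.** The gap is real: followed exactly, the plan gives a just-dosed patient a second full long-acting dose, and the data form cannot show that it happened. Under 24 h action this means 10 to 20 h of joint basal action for a home dose taken 12 to 2 h before infusion start, against none at the site's mean usual-care timing. Duration of action is an outside assumption; neither the proportion on home basal insulin nor the time of their last dose is given.

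Because the extra overlap falls under a titrated infusion, this is a small, avoidable safety exposure that should be corrected cheaply. Post-infusion overlap should not be counted as harm from the study dose. Nor should a reader infer bias in the treatment comparison or a loss of power in the plan as it stands: dosing follows the randomized assignment, and the power statement does not depend on this point.

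**What to change.** 1. Record the last home basal product, amount and date/time, with an option for unknown, in both arms before randomization, on the screening checklist and the data form.
2. Add to Intervention group-specific one short cut-off, agreed in advance with Endocrinology (for example 6 h before infusion start, an assumption). If the last dose falls within it, defer the study dose until the next home dose is due or the site's transition criteria are met, whichever is first. Treat unknown as not recent. Amend the Inclusion Criteria and Enrollment so that deferral is neither ineligibility nor a deviation.
3. Keep deferred patients in the arm to which they were randomized, analyzed by intention to treat, with the primary test unchanged.
4. Add overlap with a pre-admission basal dose to Risks and Benefits.

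The rule removes overlap during the infusion; it does not reduce post-infusion overlap at a given stop time.

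**Cost.** One more history item inside a tight window, sometimes unobtainable in confused patients. Deferred patients lose most of the timing contrast: with a 24 h dosing interval, a home dose taken 2 or 6 h before infusion start puts the deferred dose at 22 or 18 h, or sooner at transition, against 22.4 h in usual care. If a share p of the 66 were deferred and gained nothing, the others would need 6.5/(1 − p) hours for the same average difference:
- p = 5% (about 3 patients): 6.5/0.95 = 6.8 h
- p = 10% (about 7): 6.5/0.90 = 7.2 h
- p = 25% (about 17): 6.5/0.75 = 8.7 h

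The share is unknown. If arrival were uniform over a 24 h dosing interval and 25% to 100% of home users had taken their latest dose, 6/24 of those, or about 6% to 25% of home users, would fall within a 6 h cut-off; the share of the whole arm would be no higher.

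A table of hypoglycemia by recent-dose status is optional and too small to be informative: zero events in 7 patients would still allow a true rate up to 1 − 0.05^(1/7) = 35% (one-sided 95%).

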#### Control group-specific

If the patient is in the standard of care (control) group, no orders for SC insulin glargine will be placed for research purposes. A consent note and research FYI flag will be placed in the patient’s EMR to alert care teams of study

participation and to emphasize the importance of adhering to the Regions Hospital DKA Protocol, namely, to not administer long-acting insulin until patient meets all criteria as per Regions Hospital DKA Protocol. In the intervention group, the patient will have all of the same labs and medications as they would if they were in the control group or if they were not in the study at all. If they are in the intervention group, the timing of SC insulin will be earlier than it would if the patient were not in the study, but all components of the protocol are identical regardless of arm or study participation.

Various measures will be taken to promote care team compliance with the hospital DKA protocol in the control group. These include education of ICU and ED providers, including pharmacists and RNs and careful instructions to follow the SOC protocol (with exceptions for the experimental arm) in the FYI flag and consent note. Furthermore, CCRC research interns will be involved in each enrollment to ensure that insulin glargine is given in the study time window and that SOC labs are completed per the DKA Protocol. Finally, ED pharmacists are on service 24 hours per day and will be available for study patient oversight.

